Though there no adverse risk responses were reported in published

randomized controlled trials in clinical populations in the literature, there are some expected transient perceptual type responses, e.g. dizziness, limb numbness, perceived exertion, delayed onset muscle soreness. There are no significant risks of complications if BFR-RE is prescribed by certified trainers who have knowledge of appropriate protocols and contraindications to the use of occlusive stimuli. (Brandner, 2018)

The effect on muscle strength in COPDAE inpatients, which is not well studied in the literature, will be the primary outcome of this study. The effect on mobility functions, systemic muscle strength reflected by hand grip strength, health related quality of life and unplanned readmission rate within 1 month of discharge for COPDAE will be evaluated as secondary outcomes. Since BFR-RE is newly introduced to Haven of Hope Hospital and not widely used in Hospital Authority, acceptability and feasibility of this training will be explored as secondary outcomes.

Subjects

Patients with COPD acute exacerbation (COPDAE) will be recruited to find out the effect of blood flow restriction resistance exercise (BFR-RE). There will be a control group without BFR-RE for comparison. Principal investigator will screen the medical fitness of the subjects before recruiting to the study.

Inclusion criteria

1. COPD acute exacerbation (COPDAE) as the primary diagnosis for hospitalization or transfer to pulmonary wards of the Haven of Hope Hospital
2. Able to walk under supervision
3. Understand instruction in Cantonese and can give informed consent.

Exclusive criteria (Hick, 2013)

Subjects will be excluded if they have any of the following conditions:

1. Concomitant acute cardiac event	7. History of lymphectomies
2. Severe hypertension (BP > 180/100)	8. Extremities with dialysis access
	9. Vascular grafting

3. History of venous thromboembolism
4. History of peripheral vascular disease
5. Absence of posterior tibial or dorsalis pedal pulse
6. History of revascularization of the extremity
10. Current extremity infection
11. Active malignancy*
12. Open fracture / soft tissue injuries
13. Amputation to the lower extremity
14. Expected hospitalization less than 2 weeks on admission
15. Medications known to increase clotting risks
16. Isolation / Contact precaution requirement (e.g. MRSA status, CD toxin +ve status, etc.)

*Active malignancy (Kearon,2016) is defined as follow:

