- (1) not received potentially curative treatment; or
- (2) there is evidence that the treatment has not been curative (e.g. recurrent or progressive disease); or
 - A treated cancer is cured should be made by an experienced clinician, with the decision requiring a disease-free interval of follow-up.
- (3) treatment is ongoing.

Standardized 2-week in-patient rehabilitation

- Breathing exercises,
- Bronchial hygiene,
- Health education,
- Bike exercise for 20 minutes (excluding history of hip operation done)
- Walking exercise at least 50m or as tolerated
- Activity of daily living training by Occupational Therapists
- Dietitian referral if needed, to ensure adequate nutrient intake.

A standardized resistance training (Patterson, 2019)

- Exercise: Isotonic knee extension
- Sessions per week: 6 (Except Sunday and public holiday)
- Duration of intervention: 2 weeks
- Total number of sessions during hospitalization: 12 sessions
- Sets per session: 4 (Total Repetitions: 75reps in total across 4 sets)
- Rest between sets: 30s
- Execution speed: 1-2s
- Load: 15-30% of 1 repetition maximum(1-RM) (Loenneke, 2012)

- Involvement of limb per session: Alternate limb training on alternate day
- Execution: until planned rep scheme is completed or contraction failure
- Remarks: If at any time the patient becomes dizzy, severe discomfort (e.g. pain, numbness), training will be stopped.

The BFR-RE intervention group (Patterson, 2019)

The participants will have the above-mentioned resistance training with “BFR-device” with details as follows:

- Cuff size: medium
- Restriction time: 5- 10 mins (stop after finishing 4 sets of training or terminating by Physiotherapists)
- Applied location: alternate quadriceps in consecutive day
- Applied pressure: 80% limb occlusion pressure (LOP)

Control group

Same standardized 2-week in-patient rehabilitation and same amount of the above-mentioned resistance training without the “BFR device”.

Determination of maximal voluntary isometric contraction (MVIC) (Hul, 2004)

- Maximal voluntary isometric contraction (MVIC) is the simplest way to measure the force-producing capabilities of a muscle group objectively during its isometric contraction condition which means muscle group under contraction with a constant velocity of joint motion and muscle length. (The National Isometric Muscle Strength (NIMS) Database Consortium, 1996)

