The individual participant can withdraw from the study at any time. Participants

may also be excluded from the study at any time based on the investigator's evaluation.

Data registration

All data relevant for the study are recorded in a specific form.

Data of each enrolled participant are listed in a personal form.

Recruitment

Consecutive patients will be recruited in the three pulmonary wards in Haven of Hope Hospital between 10.6.2020 – 28.2.2021. The study will be expected to finish within 9 months or earlier if the expected recruitment achieved.

Expected Benefits

BFR-RE may improve the muscle strength of the knee extension and muscle size of quadriceps in the patients undergoing early rehabilitation for COPDAE. This may allow patients to actively participate the resistance training to improve the mobility function, subsequently health-related quality of life.

Adverse events

In this context, adverse events are defined as any unintended, unfavorable finding, symptom or disease that can be connected to the strength training, whether it is deemed to have a correlation with this or not. Adverse events are recorded by spontaneous registration as well as by open questioning.

Concerns on patient's safety

Delayed onset of muscle soreness (DOMS)

DOMS is normal after exercise, including after LL-BFR training. It was reported in 40% of participants in a survey before but this will subside within 24-72 hours (Patterson, 2018).

Numbness

Incidence of transient numbness is between <2% (Nakajima, 2006) to 18.5% (Patterson, 2018). This is related to the tourniquet pressure causing peripheral nerve compression.

Central vascular response

Continuous BFR-RE (keep restriction during rest period between sets) will

increase the heart rate (HR), systolic blood pressure (SBP), diastolic blood pressure (DBP), or double product (HR x SBP) compared with same exercise in free flow conditions.

Cardiac output is not affected by BFR during exercise since HR increases and stroke volume decreases proportionally compared to non-BFR groups. Changes in central hemodynamic response are blunted after BFR-RE when compared to HL-RE. However, there was reported to be 14.6% of fainting / dizziness related to BFR-RE (Patterson, 2018). The study is not blinded to the physical therapists; thus, the identification of any safety issues will be easy.

Venous thromboembolism (VTE)

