The incidence rate of VTE in general population in Asia was 0.2-0.26% (Klatsky, 2000). However, there are minimal adverse events related to this possible complication reported in BFR-RE literature. Most studies use blood markers to assess the risks of VTE BFR-RE. There is no rise in D-dimers, prothrombin fragment, thrombin-antithrombin III complex, C-reactive protein immediately after BFR-RE training or weeks after training (Madarame, 2013). The reported incidence rate of venous thrombus in a large epidemiologic questionnaire (Nakajima, 2006) in Japan was 0.055% and pulmonary embolism was 0.008%.

Moreover, BFR-RE demonstrated a stimulation of fibrinolytic system by increased tissue plasminogen activator (t-PA), a thrombus-degrading protein in the epithelial cells in healthy participants (Nakajima, 2007).

Other vascular concerns (Patterson, 2018)

There are reported superficial thrombophlebitis (0.8%) and subcutaneous hemorrhage (0.8%). Bruising was reported to be 13.1% (Nakajima, 2006).

Rhabdomyolysis

It is a clinical syndrome due to skeletal muscle damage and the release of potentially toxic substances into the circulation. The reported risk was between 0.07-0.2% (Thompson, 2018). The survey (Nakajima, 2006) in Japan revealed the low incidence of 0.008%. However, this risk was not extraordinarily higher than traditional HL-RE training.

Education

Observations and measurements are carried out by physiotherapists,

occupational therapists, doctors associated with the project.

Serious adverse events

In this context, serious adverse events are defined as events or reactions that cause:

- Death
- Life-threatening situations
- Urgent transferal to acute hospital or prolongation of existing hospitalization
- Permanent or severe disability/incapacity

Serious adverse events must be evaluated by the investigator for possible correlations with treatment in the intervention group, to consider whether there is a reasonable possibility that the adverse event has been caused by that.

The following factors are included in the evaluation:

- Consistency of time.
- Conformity with known effects of the treatment.
- Alternative reasons.

If a serious adverse event is considered to have a causal correlation with the treatment, the investigator must consider the study to be terminated ahead of time.

Ethics

The study will be conducted in accordance with the principles of the Helsinki Declaration.

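### Foreseeable cuff symptoms are not asked about in a standard way in both arms, so their rates may be undercounted and unequal capture between arms cannot be excluded

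*Combined protocol and SAP*

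**What the plan says.** The Adverse events section states how events are found: "Adverse events are recorded by spontaneous registration as well as by open questioning". It gives no symptom list, schedule or grading, and does not say who asks. Data analysis contains no adverse event analysis.

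Elsewhere the protocol names the symptoms in advance:

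- The Introduction says "there are some expected transient perceptual type responses, e.g. dizziness, limb numbness, perceived exertion, delayed onset muscle soreness".
- Concerns on patient's safety gives figures from other surveys. On muscle soreness: "It was reported in 40% of participants in a survey before but this will subside within 24-72 hours". On dizziness: "there was reported to be 14.6% of fainting / dizziness related to BFR-RE". Numbness is put at below 2% to 18.5%, and bruising (under Other vascular concerns) at 13.1%.
- The remarks to the standardized resistance training, which both arms receive, say "If at any time the patient becomes dizzy, severe discomfort (e.g. pain, numbness), training will be stopped". Whether a stopped session is recorded is not stated.

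Pain, on a visual analog scale before, immediately after and 5 minutes after exercise, is the only symptom scored at set times. Reasons for drop-out are a feasibility outcome.

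Under Blinding, participants, doctors, nurses and treating physiotherapists know the arm. Separate physiotherapists, unaware of the arm, do the assessments at recruitment and discharge. The Central vascular response paragraph treats the therapists' knowledge of the arm as a help in spotting safety problems.

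**The concern.** When the likely side effects are known beforehand, a fixed question put to everyone is the usual way to count them. Volunteered reports and open questions depend on what the patient thinks worth mentioning and what the listener thinks worth writing down. Two separate problems can follow.

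1. **Undercounting.** Dizziness and numbness are described as transient, and mild episodes are easily left unmentioned.
2. **Unequal capture.** Staff who see the cuff, and have been told what it may cause, may listen differently in the two arms. The adverse event definition leaves room for this, because it covers findings that can be linked to the training. Dizziness after exercise in a control patient may be put down to COPD. The causality review of serious events is likewise worded for the intervention group only.

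At stake is the safety description of a method that the Introduction calls new to this hospital and not well studied in these inpatients. The strength outcome is not at stake.

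**Working it through.** **Inputs from the protocol.** Total 48 patients (Sample size calculation). The plan's figure is reproduced by 18 × 1.3 = 23.4, rounded up to 24 per arm, and 2 × 24 = 48. Survey figures: dizziness 14.6%, numbness below 2% to 18.5%, bruising 13.1%, soreness 40%. The protocol has no calculation of its own for adverse events.

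**Assumptions.** Allocation is 1:1. The survey figures are read as per-patient risks over the course. Capture *s* is the share of affected patients who are recorded. The documents give no value for it, so a range is shown.

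**Step 1: recorded cases in the BFR arm, 24 × p × s.**

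| Symptom | p | s = 100% | 75% | 50% | 25% |
|---|---|---|---|---|---|
| Soreness | 40% | 9.6 | 7.2 | 4.8 | 2.4 |
| Numbness, upper figure | 18.5% | 4.4 | 3.3 | 2.2 | 1.1 |
| Dizziness | 14.6% | 3.5 | 2.6 | 1.8 | 0.9 |
| Bruising | 13.1% | 3.1 | 2.4 | 1.6 | 0.8 |
| Numbness, taken as 2% | 2% | 0.5 | 0.4 | 0.2 | 0.1 |

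**Step 2: chance that no case is recorded, (1 − p·s)^24.**

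- Dizziness: 0.854^24 = 2.3% with full capture; 0.927^24 = 16% at half capture.
- Numbness at 18.5%: 0.7% and 10%. At 2%: 62% and 79%, so at the low figure an empty table is likely however the question is asked.
- Bruising: 3.4% and 20%.
- Soreness: close to 0 and 0.5%.

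If only 18 BFR patients are counted, the dizziness figures are 5.8% and 26%.

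**Step 3: effect on the comparison.** If the true rates are equal, the recorded rate ratio is s(BFR) / s(control).

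- 50% in both arms: 0.50 / 0.50 = 1.0.
- 90% against 50%: 0.90 / 0.50 = 1.8.
- 75% against 25%: 0.75 / 0.25 = 3.0.
- The other way round, 50% against 90%: 0.50 / 0.90 = 0.56.

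So undercounting lowers the rates but does not by itself distort the ratio. Unequal capture does, in either direction.

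**Step 4: what complete capture would achieve.** The exact 95% interval for 4 of 24 is 4.7% to 37.4%, and for 3 of 24 it is 2.7% to 32.4%. Power of a two-sided Fisher test with 24 per arm, against a true control rate of 0%, is 47% for numbness at 18.5%, 27% for dizziness and 20% for bruising. For soreness it is 99% against 0%, but controls do the same exercise; against a control rate of 10% it is 60%.

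**The case against.** A reader might infer that these symptoms will be undercounted, that the arms will not be comparable, and that all reports come through unblinded staff. The documents do not support that much.

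- No capture rate is given. Forewarned staff could over-record in the BFR arm as easily as under-record.
- Equal undercounting leaves the rate ratio at 1.0 (Step 3).
- The person who asks is not named. Blinded physiotherapists see patients at discharge, and the protocol does not say whether they ask about events.
- The percentages come from other surveys and are not this plan's predictions. Numbness may be below 2%, and bruising is not among the responses that the Introduction calls expected.
- Tolerability as such is not a listed outcome. Acceptability means pain score and liking; feasibility means drop-out and its reasons. No test of adverse events between arms is planned.
- Some cover exists. The stopping remark applies to both arms, drop-out reasons are examined, and pain scoring around exercise brings staff and patient together when brief symptoms occur.
- A checklist cannot blind the participant, and the trial is too small for a precise comparison (Step 4).

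All of this stands, and it limits the point to the quality of the safety description. It does not close the gap. Recording of stopped sessions is not specified, and symptoms too mild to stop a session or cause drop-out escape both safeguards. Nothing in the plan puts the same question to both arms.

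**Conclusion.** The point holds as a weakness of method. Symptoms that the protocol itself names in advance are left to volunteered reports and open questions, in a trial where participants and treating staff know the arm. Their rates may be undercounted, and a difference between arms could reflect unequal recording. Neither is certain, and the direction of any bias is unknown.

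The size depends on capture rates that the documents do not give. At half capture, about 1.8 of 3.5 dizziness cases would be recorded, and a table with none would arise about one time in six. The numbness illustration depends on using the upper figure. The false ratio of 1.8 depends on the assumed 90% against 50% split. All figures assume 1:1 allocation and survey rates read as per-patient risks. The primary result and the sample size are untouched. This is a cheap improvement to the safety data, not a flaw that threatens the trial.

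**What to change.** Keep volunteered reporting and add a fixed yes/no list with a severity grade: dizziness or faintness, limb numbness, muscle soreness, bruising, leg swelling. Read it out in identical words to both arms at each session alongside the pain score, covering the time since the last session so that later soreness and bruising are included. Have the blinded assessor ask it once more at discharge. State who asks.

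Report the number of patients per arm with each item, descriptively and with exact 95% confidence intervals, separately from volunteered events.

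The cost is one block of items on the study forms and a short time per session. Counts will rise in both arms because patients are prompted. Answers from unblinded participants remain open to some reporting bias, and the comparison between arms stays imprecise (power about 20% to 47% for bruising, dizziness and numbness even against a 0% control rate). The documents do not say how the cited surveys counted events, so the new rates should not be set directly against those figures.
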